### ***Rationale for 24 Months Maximum Treatment Duration***

The optimal duration of treatment by checkpoint blockade inhibitors in oncology is currently unknown. However, given their mechanism of action continuous treatment may not be required as opposed to targeted agents or most of cytotoxic therapies.

With almost a decade of experience using CTLA-4 and PD-1/PD-L1 inhibitors, accumulating evidence from different clinical trials in different tumor types indicates that most of the

---

CONFIDENTIAL

*This document is confidential. Do not disclose or use except as authorized.*

IRB APPROVED

responses are generally occurring early, with a median time to response of 2 to 4 months including in patients with NSCLC, and most of the responses are likely to be durable as compared to conventional therapies.

Limited duration of therapy was explored in few trials, for instance, ipilimumab the first checkpoint blockade inhibitor targeting CTLA-4 was initially approved in metastatic melanoma in participants who failed standard of care chemotherapy. This approval was based on overall survival improvement after a limited duration of ipilimumab therapy, including only 4 induction doses for a duration of treatment of 12 weeks, with a sustained plateau in survival starting at around year two. Moreover, in Checkmate 003 a dose-escalation cohort expansion trial evaluating the safety and clinical activity of nivolumab in patients with advanced solid tumors implemented stopping nivolumab monotherapy at 96 weeks (~ 2 years). At 2 years, 16 NSCLC participants who were on still on therapy discontinued nivolumab per protocol, of these, 75% of patients (n = 12) were alive > 5 years and did not receive further therapy after stopping nivolumab and remained progression free.

Moreover, long-term follow up data from study KeyNote-006 a phase 3 Melanoma study demonstrates that pembrolizumab provides durable efficacy after stopping the protocol-specified duration of treatment at 2 years. The median follow-up was of 33.9 months, among the 104 (19%) participants who completed pembrolizumab, median exposure was 24.0 months. After additional median follow-up of 9.0 months after completion of pembrolizumab, 102 (98%) pts were alive and responses were durable in pts who completed pembrolizumab.

In addition, data from different series are showing that patients receiving immunotherapy-based treatment may discontinue treatment due to safety events. In a recent analysis in a melanoma study the majority of patients who discontinue nivolumab and/or ipilimumab for toxicity maintain disease control in the absence of further treatment.

CheckMate 153 is the first randomized study to evaluate treatment duration with a PD-1/PD-L1 inhibitor. In this study, progression free survival appears to be durable with a plateau at 2 years from first dose including in pts who stopped nivolumab after 1 year, suggesting the risk of progression after 2 years of treatment is minimal, even in the absence of further treatment, which is consistent with existing data with PD-1/PD-L1 datasets. In addition, 34 out of 87 patients with clinical benefit who stopped therapy at 1 year were retreated upon progression as per protocol, in this group, nivolumab retreatment did not appear to re-induce responses and in the majority of the cases, the tumor continues to progress suggesting that treatment change, using preferentially an agent or approach with a different MOA.

Collectively, these data suggest that there is likely no benefit from treatment beyond two years in advanced tumors. However, even though immunotherapy is well tolerated, patients will be exposed to the risk of additional toxicity with longer-term treatment. Therefore, in CA209-651 treatment with nivolumab +/- ipilimumab will be given for up to 2 years from start of treatment.

## 2.4 Correlative Studies Background

Correlative studies are an integral part of this protocol to gain insight into the basic biologic

---

CONFIDENTIAL

*This document is confidential. Do not disclose or use except as authorized.*

IRB APPROVED

response to PD-1 and CTLA-4 blockade in thyroid cancer and the early identification of mechanisms of drug resistance. The purpose of the randomized lead-in phase with Nivolumab and ipilimumab starting sequentially is to provide opportunities to study the specific immunologic changes that occur in response to either drug alone as well as both drugs in combination. The clinical endpoints are assessed during treatment with both drugs combined.

Recently, a novel method for evaluating ex vivo response to immune checkpoint blockade using patient-derived organotypic tumor spheroids (PDOTS) cultured in a 3-dimensional microfluidic system has been developed. It could be demonstrated that spheroids isolated from fresh human tumor samples retain autologous lymphoid and myeloid cell populations, including antigen-experienced tumor infiltrating CD4/CD8 T lymphocytes, and survive in extracellular matrix. PD-1 and CTLA-4 blockade inhibition across a large panel of PDOTS including samples from 4 thyroid cancer patients consistently showed up-regulated homeostatic lymphokines involved in T- and B- cell chemoattraction, demonstrating the feasibility of ex vivo profiling of PD-1 and CTLA-4 blockade, it could also be demonstrated that induction of a dysfunctional cytokine response may contribute to intrinsic resistance. (Jenkins *et al.*, *Nature*, under review).

We have tested samples from 4 patients with thyroid cancer and found that treatment of spheroid cultures with CTLA4, and to a lesser extent with PD-1 blockade led to the rapid cell death of thyroid cancer cells. These studies along with early reports to PD-1 and CTLA-4 blockade are the basis for this protocol.

Patients will be required to undergo sequential biopsies, if accessible tumor is present. Tumor samples will be grown in the microfluidic chamber system and tumor infiltrating lymphoid and myeloid cells will be analyzed both in vitro and by flow cytometry across several samples obtained prior to treatment, during treatment with nivolumab or ipilimumab and with both drugs combined. This will allow us to determine optimal sequencing of the 2 drugs, and potential mechanisms of resistance during treatment.

Circulating tumor cells (CTCs) may reflect the ongoing molecular evolution of thyroid cancer cells and reveal molecular and genetic changes that confer migration and invasion advantages. It is essential to define mechanisms of resistance at more than one timepoint. This is important because resistance mechanisms may be completely different at different stages of disease, but difficult to achieve with tissue biopsies. The goal of this exploratory endpoint is to understand how tumor heterogeneity evolves during progression of thyroid cancer, and with development of resistance/refractory disease. The objective is to determine the transcriptional profile of CTCs, myeloid and lymphoid WBC's in peripheral blood and compare to cancer and tumor infiltrating lymphoid and myeloid cells in tissue biopsies through RNA sequencing, and to define how these change with therapeutic intervention over time. Recent advances in next-generation sequencing and single cell isolation techniques will make this a minimally invasive approach to perform comprehensive genomics in patients with thyroid cancer to inform clinical treatment decisions.

In addition to CTCs, other circulating biomarkers can be detected in plasma and serum, such as cell-freeDNA (cfDNA), microvesicles and exosomes. Some of these markers have been found to correlate with increasing tumor burden and treatment response in various types of malignancies. cfDNA, and nucleic acids in microvesicles and exosomes in cancer subjects can harbor many

---

CONFIDENTIAL

*This document is confidential. Do not disclose or use except as authorized.*

IRB APPROVED

genetic alterations (mutations, microsatellite alterations, aberrant methylation), which are generally consistent with the tumor. Thus, blood may be a useful surrogate for tissue, and can be especially valuable at time points or in disease settings where tumor tissue collection may be challenging to evaluate drug response, resistance and disease progression.

In addition, cell sorting of peripheral CD4 and CD8 positive cells by flow cytometry and single cell sequencing provides an opportunity to evaluate the changes immune cells undergo in response to checkpoint inhibition with PD-1 and CTLA-4. Samples will be assessed for expression of markers of exhaustion (PD-1, CTLA-4, TIM3) and how these markers change in response to nivolumab, Ipilimumab or both drugs combined.

We have tested several peripheral blood samples from thyroid cancer patients and could document the presence of CTC's as well as cfDNA in approximately 60% of cases.

### **3. PARTICIPANT SELECTION**

Participants must meet the following inclusion criteria on screening examination to be eligible to participate in the study:

#### **3.1 Inclusion Criteria**

1. Metastatic, RAI-refractory, differentiated thyroid cancer (including papillary and follicular thyroid cancer and their sub-types such as Hurthle cell thyroid cancer as well as poorly differentiated thyroid cancer), medullary thyroid cancer, or anaplastic thyroid cancer. RAI-refractoriness is not required for medullary or anaplastic thyroid cancer patients. Patients who are not candidates for RAI therapy, as determined by the investigator, are also eligible.

RAI-refractoriness is defined as absence of uptake of RAI on either a low-dose diagnostic test or a post-treatment RAI scan in measurable lesions or radiographic progression of disease within 12 months of the last course of RAI treatment despite the recorded uptake of RAI with that previous therapy or having a cumulative lifetime administered dose of greater than 600mCi.

2. Patients must have experienced disease progression within 13 months prior to study registration, have experienced intolerable side effects on a tyrosine kinase inhibitor (TKI), or be not suitable candidates for TKI. No progression is required for patients with anaplastic thyroid cancer.
3. Age 18 years or older
4. Any number of prior treatments allowed for patients under 65y, over 65y, if suitable candidate for TKI therapy, must have at least one prior line of TKI treatment (excluding medullary and anaplastic patients)

5. ECOG performance status  $\leq 2$  (Karnofsky  $\geq 60\%$ , see Appendix A).

Measurable disease by per RECIST 1.1 criteria (see section 11). Radiographic tumor assessment performed within 28 days of registration

6. Participants must have normal organ and marrow function as defined below:

Screening laboratory values must meet the following criteria and should be obtained within 21 days prior to randomization/registration

- WBC  $\geq 2000/\mu\text{L}$
- Neutrophils  $\geq 1200/\mu\text{L}$
- Platelets  $\geq 100 \times 10^3/\mu\text{L}$
- Hemoglobin  $> 8.0 \text{ g/dL}$
- Serum creatinine  $\leq 1.5 \times \text{ULN}$  or creatinine clearance (CrCl)  $\geq 40 \text{ mL/min}$  (if using the Cockcroft-Gault formula below):

$$\text{Female CrCl} = \frac{(140 - \text{age in years}) \times \text{weight in kg} \times 0.85}{72 \times \text{serum creatinine in mg/dL}}$$

$$\text{Male CrCl} = \frac{(140 - \text{age in years}) \times \text{weight in kg} \times 1.00}{72 \times \text{serum creatinine in mg/dL}}$$

- AST/ALT  $\leq 3 \times \text{ULN}$
- Total Bilirubin  $\leq 1.5 \times \text{ULN}$  (except subjects with Gilbert Syndrome, who can have total bilirubin  $< 3.0 \text{ mg/dL}$ )

7. Ability to understand and the willingness to sign a written informed consent document.

8. Women of childbearing potential (WOCBP) must use appropriate method(s) of contraception. WOCBP should use an adequate method to avoid pregnancy for 23 weeks (30 days plus the time required for nivolumab to undergo five half-lives) after the last dose of investigational drug

9. Women of childbearing potential must have a negative serum or urine pregnancy test (minimum sensitivity 25 iu/l or equivalent units of hcg) at screening. Pregnancy test will be repeated on the day of the first dose of study drug (before administration), although results of this test are not required for registration.

*“Women of childbearing potential” is defined as any female who has experienced menarche and who has not undergone surgical sterilization (hysterectomy or bilateral oophorectomy) or who is not postmenopausal. Menopause is defined clinically as 12 months of amenorrhea in a woman over 45 in the absence of other biological or physiological causes.*

10. Men who are sexually active with WOCBP must use any contraceptive method with a failure rate of less than 1% per year. Men receiving nivolumab and who are sexually active with WOCBP will be instructed to adhere to contraception for a period of 31 weeks after the last dose of investigational product. Women who are not of childbearing

---

CONFIDENTIAL

*This document is confidential. Do not disclose or use except as indicated.*

IRB APPROVED

potential (ie, who are postmenopausal or surgically sterile as well as azoospermic men do not require contraception

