### **Differentiated Thyroid Cancer**

DTC includes papillary and follicular thyroid cancer as well as poorly differentiated histologies. Most DTC cases are usually cured with surgery, radioactive iodine (RAI), and thyroid hormone suppression therapy. Papillary thyroid cancer (PTC) is the most frequent type of thyroid cancer. Most people who develop thyroid cancer are between age 25 and 65 years. The prognosis is generally good; however, 7–23% of patients, distant metastases develop and further treatment with RAI can eradicate the disease in only one third of such cases, while two thirds develop radioiodine refractory (RAIR) disease. The 10-year survival rate among patients with RAIR DTC is only 10% (1). Currently, only two multi-targeted tyrosine kinase inhibitors (TKI) have U.S. Food and Drug Administration (FDA) approval for progressive DTC based on improved PFS compared to placebo in two large phase 3 studies. Sorafenib demonstrated a 5-month improvement in median PFS versus placebo (10.8 versus 5.8 months) in a phase 3 trial of 447 RAIR TC patients who had progressed within 14 months prior to enrollment (2). Lenvatinib, also demonstrated a significant improvement in median PFS compared to placebo (18 months versus 3.6 months) in a phase 3 trial of 330 RAIR TC patients who had progressed in the prior 13 months (3). Remarkably, neither study showed a survival benefit for the patients on the experimental arm except for those age 65 and older (4). Crossover was allowed in these studies.

Recent data suggests that PD-1 and PD-L1 are over-expressed in thyroid cancer and the amount of PD-L1 expression appears to correlate with prognosis.

The PD-1 inhibitor pembrolizumab has been tested in a phase I study that included 22 patients with PD-L1 positive metastatic thyroid cancer (5). Eighteen of these patients had previously been treated with radioiodine and were considered RAI refractory. Two out of 22 patients had a partial response (9.3%).

The goal of this study is to determine response rate in patients with RAI refractory thyroid cancer that is incurable.

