### **Medullary Thyroid Cancer**

Medullary thyroid cancer constitutes approximately 2% of cases diagnosed with thyroid cancer and is derived from parafollicular C-cells. While it may not progress even as metastatic disease for many years, most patients enter an accelerated disease phase and require medical treatment. Tyrosine kinase inhibitors Vandetanib and Cabozantinib are FDA approved for this disease based on randomized phase 3 studies which showed a significant difference in PFS but no difference in overall survival. Subgroup analysis showed that this was true for all subgroups except for those who had the RET M918T mutation. In that group, survival was improved over placebo.

Pulsed dendritic cells were used in a study to treat refractory medullary thyroid cancer and decrease in tumor markers were seen suggesting that medullary thyroid cancer may be amenable

to immunotherapy. However, no published experience with modern immunotherapy drugs has been published in medullary thyroid cancer. Given the fact that, there are no established treatment options beyond first line treatment and frequently, once patients have entered the accelerated phase, the cancer is very aggressive and response to TKI treatment is often brief.

However, no published reports have demonstrated efficacy of PD-1 or CTLA-4 directed therapy has been published.

This study will include an exploratory cohort of 7 patients with medullary thyroid cancer with any number of prior therapies (including first line in this patient population without the RET M918T mutation) to explore possible use of IO in this patient population. Exploratory cohorts (histologic subtypes) will be randomized.

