## 5.2 Pre-Treatment Criteria

Eligibility and exclusion criteria are provided in Section 3. These criteria will be assessed 21 days prior to study registration to establish eligibility and baseline values.

Informed consent will be obtained after the study has been fully explained to the subject and before the conduct of any screening procedures or assessments. If screening assessments occur within 3 days before start of study treatment, then they may serve as the baseline cycle 1 day 1 visit and cycle 1 day 1 labs do not need to be performed.

Demographic information and baseline characteristics will be collected at the Screening Visit. Standard demographic parameters include age, sex, and race/ethnicity (recorded in accordance with prevailing regulations). Baseline characteristics will include ECOG PS (Appendix A), disease status, medical histories, and prior and concomitant medications.

Additional testing required, as per Section 3, is: hematology panel (see Table 1), chemistry panel (see Table 1), coagulation panel, urine or serum HCG (in women of childbearing potential; see Section 3 for when serum HCG testing is required), TSH (with reflexive Free T4 and Free T3), Mg, LDH, amylase, lipase.

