**Table 1: Clinical Laboratory tests.**

Category	Tests
Hematology panel	

• Hematocrit, hemoglobin, platelet count, WBC with differential (bands, basophils, eosinophils, lymphocytes, monocytes, neutrophils), ANC

Chemistry Panel	

• Chloride, potassium, sodium, BUN, serum creatinine, phosphorus, calcium, albumin, total protein, alkaline phosphatase, ALT, AST, total bilirubin, glucose

---

CONFIDENTIAL

*This document is confidential. Do not disclose or use except as authorized.*

IRB APPROVED

*Abbreviations: ALT = alanine aminotransferase; ANC = absolute neutrophil count; AST = aspartate aminotransferase;  $\beta$ -hCG = beta-human chorionic gonadotropin; BUN = blood urea nitrogen; WBC = white blood cells*

---

Archival tumor sample should be collected (block or if not possible, at least 20 unstained slides). If unavailable, a baseline tumor biopsy is required, if safe to perform.

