## **5.6 Criteria for Taking a Participant Off Protocol Therapy**

Duration of therapy will depend on individual response, evidence of disease progression and tolerance. In the absence of treatment delays due to adverse event(s), treatment may continue until one of the following criteria applies:

- Disease progression
- Intercurrent illness that prevents further administration of treatment
- Unacceptable adverse event(s)
- Participant demonstrates an inability or unwillingness to comply with the oral medication regimen and/or documentation requirements
- Participant decides to withdraw from the protocol therapy
- General or specific changes in the participant's condition render the participant unacceptable for further treatment in the judgment of the treating investigator
- A maximum of 24 months from the first study treatment

Participants will be removed from the protocol therapy when any of these criteria apply (with the exception of disease progression, in which case participants may or may not be removed from protocol therapy, at the investigator's discretion). The reason for removal from protocol therapy, and the date the participant was removed, must be documented in the case report form (CRF). Alternative care options will be discussed with the participant.

When a participant is removed from protocol therapy, Treatment Ended information will be updated in OnCore by the research team.

In the event of unusual or life-threatening complications, treating investigators must immediately notify the Overall PI, [name]

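### Section 2.1 describes first-line medullary entry as being for patients without RET M918T, but criteria 2 and 4 in Section 3.1 carry no RET condition, so a TKI-naive carrier is eligible and would defer a TKI while on study treatment

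*Combined protocol and SAP*

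**What the plan says.** **Background.** Section 2.1 (Medullary Thyroid Cancer) reports that vandetanib and cabozantinib improved PFS but not overall survival. A subgroup analysis found this in every subgroup "except for those who had the RET M918T mutation. In that group, survival was improved over placebo". The same section describes the medullary cohort as patients "with any number of prior therapies (including first line in this patient population without the RET M918T mutation").

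**Eligibility.** Section 3.1 sets the binding criteria.
- Criterion 2 opens with "Patients must have experienced disease progression within 13 months prior to study registration" and then gives TKI intolerance and TKI unsuitability as alternatives.
- Criterion 4 allows any number of prior treatments under 65. Over 65, a patient suitable for a TKI "must have at least one prior line of TKI treatment (excluding medullary and anaplastic patients").
- Neither the remaining inclusion criteria nor the exclusions in Section 3.2 mention RET.

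**Screening.** Section 5.2 begins its list "Additional testing required, as per Section 3, is: hematology panel (see Table 1), chemistry panel (see Table 1), coagulation panel" and names no RET result. The tests that the Section 10 calendar adds for medullary patients are calcitonin, CEA and CA19-9.

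**On study.** Section 6.8.1 prohibits concurrent anti-neoplastic therapy. Section 5.6 caps treatment at 24 months and lists progression as a reason to stop, "with the exception of disease progression, in which case participants may or may not be removed from protocol therapy, at the investigator's discretion".

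**The concern.** The Section 2.1 parenthesis has little purpose unless TKI-naive M918T carriers are meant to stay out of first-line entry. That limit appears only in the background, where it does not decide who is registered. The criteria that do decide admit the patients whom the background describes as outside first-line entry.

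The differentiated cohort was handled differently. Section 2.1 says of the two TKI trials there that "neither study showed a survival benefit for the patients on the experimental arm except for those age 65 and older", and criterion 4 requires a prior TKI line of TKI-suitable DTC patients over 65. The subgroup finding for DTC reached the eligibility rule; the one for medullary disease did not.

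At stake is the order of treatment for a few patients. An enrolled TKI-naive carrier would put off a drug class that the protocol itself links to longer survival in that group. In its place the patient would receive a combination for which Section 2.1 says no published report has shown efficacy in medullary cancer.

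**Working it through.** The plan states no figure on this point. The check is a comparison of texts, followed by short arithmetic on scale.

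**Step 1: eligibility of the test case.** Take a medullary patient with RET M918T, no prior TKI, progression within the past 13 months, measurable disease, ECOG 0 to 2 and adequate organ function.

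| Provision | Requirement | Test case |
|---|---|---|
| 3.1, criterion 1 | Medullary histology accepted; RAI-refractoriness not needed | Met |
| 3.1, criterion 2 | Recent progression, or TKI intolerance, or TKI unsuitability | Met by progression alone |
| 3.1, criterion 4, under 65 | Any number of prior treatments, so none is acceptable | Met |
| 3.1, criterion 4, over 65 | Prior TKI line, but medullary patients exempt | Met |
| 3.2 | No exclusion mentions RET | Not excluded |
| 5.2 and Section 10 | No RET result listed | Status need not be known |
| 9.1 | Exome sequencing as a correlative | Not tied to registration |
| 2.1 | First line described for patients without M918T | Outside the description |

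The test case meets the printed criteria and conflicts only with the background.

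**Step 2: access to a TKI after entry.** Section 6.8.1 rules out other anti-neoplastic therapy during study treatment. A TKI is therefore deferred until the patient comes off protocol therapy.

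**Step 3: length of the deferral, counted from first dose.** Inputs are a first on-treatment scan at week 9, scans every 8 weeks or as clinically indicated (Section 10), and the 24-month cap (Section 5.6).
- Progression at the first scheduled scan and treatment stopped: week 9 minus week 1 = 8 weeks. A clinically indicated scan, or withdrawal, could make this shorter.
- Treatment continued past that scan and stopped at the next: 8 + 8 = 16 weeks.
- Outer limit: 24 months, about 104 weeks, or 104/8 = 13 scan intervals. This is reached mainly with disease control or judged benefit.

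**Step 4: number of patients.** Section 13 plans 7 medullary patients among 54 entries: 7/54 = 0.130, or 13%. That is the share of the whole medullary cohort, not of affected patients. The documents give neither the M918T share nor the TKI-naive share, so the count of TKI-naive carriers lies between 0 and 7 and no probability can be attached.

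**Step 5: effect on the primary analysis.** The primary efficacy population in Section 13 is DTC only (23 patients, then 32). Medullary patients do not enter the two-stage rule.

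**The case against.** **The background may be the text that is wrong.** Section 2 has not been fully maintained. Section 2.1 still says the exploratory cohorts will be randomized, while Sections 1.1, 5.1 and 13 say anaplastic patients are not. The RET parenthesis could be a similar leftover. Criterion 4 exempts medullary patients in the same sentence that sets the TKI rule, which can be read as deliberate. This stands as a real possibility. It changes which text to correct, not whether the two disagree.

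**The reason is inferred.** Section 2.1 never says that the survival subgroup is why first-line entry is described for patients without M918T. The two statements are close together and no other reason is offered. The parenthesis also does not say in terms that carriers need a prior TKI. This stands.

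**Harm is not shown.** A reader might infer that enrolled carriers lose a survival benefit. The documents do not support that. The evidence is one subgroup sentence with no citation, which does not say which TKI showed the effect. Section 2.3 repeats the absence of a survival difference without any exception. The comparison was with placebo, and nothing supplied shows that the benefit is lost when a TKI follows immunotherapy.

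**Safeguards exist.** Scans can be brought forward and a patient may leave therapy. Treatment past progression under Section 5.6.1 needs judged clinical benefit, no rapid progression, no delay to an imminent intervention against serious complications, and fresh consent covering alternatives. An investigator may also decline to enroll a known carrier. These points limit the deferral but do not close the eligibility gap. The checklist reviewed by the registrar (Section 4.1) and the consent pages are not in the supplied text, so a RET item there cannot be ruled out.

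**Conclusion.** The inconsistency is real and worth correcting. As printed, Section 3.1 admits a TKI-naive medullary patient with RET M918T and recent progression, whom Section 2.1 describes as outside first-line entry, and that patient defers a TKI while on study treatment.

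The size is small and partly unknown: 0 to 7 patients in an exploratory cohort. The deferral is about 8 weeks if treatment stops at the first scheduled scan and at most 24 months. The DTC response analysis, sample size and stopping rule are untouched.

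The conclusion assumes that the Section 2.1 parenthesis reflects current intent and that the unseen checklist adds no RET condition. Two further inferences go too far: that the plan is shown to harm carriers, and that it must require a new RET test before registration. Section 2.1 calls for no such test. Requiring one could add a procedure or shut out patients without usable tissue.

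**What to change.** Limit the medullary exemption in criterion 4, for example by adding: *Medullary patients known to carry RET M918T who are suitable candidates for a TKI must have had at least one prior line of TKI treatment.* The suitability clause is not in Section 2.1; it mirrors the condition that criterion 4 already applies to DTC patients over 65. On the eligibility checklist, record any available RET result for TKI-naive medullary patients.

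A new RET test before registration should be optional. A site that wants one could use tissue already called for in Section 5.2: "Archival tumor sample should be collected (block or if not possible, at least 20 unstained slides").

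The cost is one sentence and one checklist item. A known TKI-naive carrier who is suitable for a TKI could no longer enter first-line, which may slow medullary accrual slightly. Carriers whose status is unknown could still enter; that is the price of not requiring a test.

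If the sponsor does intend to admit TKI-naive carriers, leave Section 3.1 as it is, correct the Section 2.1 description and state the reason.
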